#### *Safety regarding chest tube management*

Despite single center studies proving the safety of early chest tube removal, no randomized data are available to compare early with late chest tube removal. Furuya specifically evaluated chest tube duration in a cohort and showed that in 85% of patients operated for PSP the chest tube could safely be removed on the same day of surgery with only 1 patient (1%) needing reinsertion of the chest tube within 1 week (5). Lacking high level of evidence studies on this topic, we performed a systematic review comparing recurrence rates between studies with early (6 studies, n=501) and late (17 studies, n=2,138) chest tube removal. The data demonstrate recurrence rates of 4.59% versus 5.57% for early and late chest tube

management respectively, with acceptable heterogeneity ( $I^2=36%$  and  $I^2=42%$ ).

Furthermore, early chest tube removal proved also to be safe regarding complications, such as prolonged air leak and hemothorax, which were even slightly favorable after early removal. In addition, a Dutch survey among thoracic surgeons indicated that 31% of Dutch hospitals already apply early chest tube removal when air leakage is absent (9).

#### *Intervention for pain management*

Before surgery, the skin of the incision site(s) will be injected with a local anaesthetic. At the beginning of surgery, before pleurectomy, a single shot PVB will be placed at 10 levels (T2-T11) by the surgeon with a local anaesthetic and 2-3mL per site under direct thoracoscopic vision. The injection site will be chosen at the paravertebral space, just lateral adjacent to the sympathetic trunk. This group will have no analgesic catheters for continued analgesia with local anaesthetics. No mobility restrictions are needed and no bladder catheter is given.

#### **5.4 Escape medication**

If following awakening from anaesthesia in the recovery room the patient experiences inadequate pain control (NRS  $\geq 4$ ) and a bolus of epidural infusion via de epidural catheter is insufficient, opioids will be given until a maximum dose specified by the attending anaesthesiologist. If insufficient pain control is achieved, additional clonidine 1  $\mu\text{g}/\text{kg}$  or esketamine (depending on patient's hemodynamics and local protocol) is injected intravenously in order to obtain adequate pain control (NRS  $<4$ ). If the above regime does not result in adequate pain control additional interventions will be administered at the discretion of the attending anaesthesiologist, with the exception of NSAIDs that are not allowed. All analgesic medications and interventions given will be registered in the CRF.

#### **5.5 Postoperative pain medication**

A multimodal analgesic regime will be provided to each patient and will consist of paracetamol (acetaminophen) 4 times a day 1000 mg and oxycodone 6 times a day 5-10 mg as needed. The abovementioned regime applies only for patients in the control group if TEA is removed or when there is no opioid in the TEA solution anymore. All analgesic medications and interventions will be registered in the CRF.

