### *Usual care for pain management*

For usual care, a TEA catheter will be placed in the awake patient after local anaesthesia of the skin. After correct placement of the epidural catheter at the 4th or 5th intervertebral space, a local anaesthetic (ropivacaine, levobupivacaine or bupivacaine) will be started with an additional opioid to the epidural solution according to in-house protocols. Before surgery, the skin of the incision site will be injected with a local anaesthetic. In the nursing ward, patients are allowed to mobilize under supervision when the motor function and sensibility of the

extremities allows it. Placement of a urinary catheter will be left to in-house protocols, however placement will be registered in the CRF. A provisional stop of the administration of the epidural infusion is planned after 48 hours (on the second postoperative day). In case NRS pain scores are  $\geq 4$  despite additional pain medication, the TEA can stay in place and the epidural infusion is resumed after a bolus of 5 mL of the epidural infusion fluid. After administration of the epidural infusion bolus, the vital signs of the patient are controlled for at least 30 minutes. Subsequently, NRS pain scores will be assessed daily until pain management is sufficient and the TEA can be withdrawn, with a maximum of 4 days. If rescue attempts to the epidural anaesthesia fail to improve pain scores, opioids may be withdrawn from the epidural solution and oral or intravenous opioids will be supplied. In case an accidental spinal puncture during placement of the TEA catheter occurs, the patient is not considered eligible for the TEA technique. In this case, a single-shot PVB is placed instead (see *intervention for pain management*). In case the epidural catheter is accidentally removed or is not placed correctly, the patient will receive systemic analgesia. This is already routine in usual care.

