### **8.3 Study procedures**

Preoperatively, during the process of informed consent, patients will be asked to complete a baseline QoR-15 questionnaire, QLQ-C30, EQ-5D health status, and baseline adjusted iMTA questionnaire. A preoperative CT-scan will be made to rule out possible secondary causes of pneumothorax in case a prior CT scan of the last 5 years is not available, which is standard of care.

The surgical procedures are described under paragraph 5 *'treatment of subjects'* and are part of standard general health care. In case of a pleurectomy, a total pleurectomy will be performed. In case of chemical pleurodesis, the entire pleural surface will be sprayed with talc. All procedures will be performed by VATS (either 1, 2 or 3 incisions). After surgery one postoperative chest tube will be placed mid-thoracic and a Thopaz system is used which is set at a threshold of -2cm H2O (or -5cm H2O). A chest X-ray will be performed ultimately 4 hours after surgery or in the morning of POD1 which is also part of routine postoperative care. In case all chest tube removal criteria are met (*see paragraph 5.2 'usual care' and 5.3 'interventions'*), the chest tube will be removed during expiration.

Regarding postoperative analgesia, the TEA catheter is placed preoperatively in awake patients and will be left in place for at least 2 days after surgery (*see paragraph 5.2 'usual care'*). Patients are allowed to mobilize under supervision when the motor function and sensibility are intact. The need for a urinary catheter will be in accordance with in house protocols of the participating hospital. In case of a single-shot PVB, patients will receive a single shot of 2-3 mL local analgesic in the paravertebral space per intercostal level from T2-

T11 (see paragraph 5.3 'interventions'), corresponding to a total volume of 20mL. The PVB will be placed perioperatively before performing pleurectomy. No urinary catheter or mobilisation restrictions are needed with single-shot PVB. Oral painkillers will include paracetamol, oxynorm and oxycontin. NSAIDs will not be allowed.

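### Section 5.5 words the TEA exception too broadly: as written it withholds scheduled paracetamol, not only oxycodone, from TEA patients while an opioid-containing epidural runs

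*Protocol*

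**What the plan says.** Section 5.5 opens without restriction: "A multimodal analgesic regime will be provided to each patient". The regime has two parts, scheduled paracetamol (1000 mg four times daily) and oxycodone (5-10 mg up to six times daily, as needed). The next sentence restricts the regime as a whole: it "applies only for patients in the control group if TEA is removed or when there is no opioid in the TEA solution anymore".

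Section 5.2 (usual care for pain management) describes the epidural. The local anaesthetic "will be started with an additional opioid to the epidural solution according to in-house protocols". On duration: "A provisional stop of the administration of the epidural infusion is planned after 48 hours (on the second postoperative day". Extension is possible to a maximum of 4 days. Section 8.3 agrees: "the TEA catheter is placed preoperatively in awake patients and will be left in place for at least 2 days after surgery".

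The outcome affected is the second primary outcome in section 8.1.1, the proportion of NRS scores of 4 or more over POD 0-3. It is tested for non-inferiority of PVB to TEA, with at least 11 scores per patient.

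**The concern.** The restriction is tied to opioid in the epidural, which is a sensible reason to hold back oxycodone but not paracetamol. Because the sentence refers back to the full regime, it takes both drugs away from TEA patients during the planned infusion, and it conflicts with the opening statement that each patient receives the regime.

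This matters because TEA is the comparator in a non-inferiority test. If a background analgesic is given in the PVB arms and withheld in the TEA arms, the comparator may do worse for a reason unrelated to the two techniques, and that component of the difference moves towards non-inferiority. If some sites follow the letter and others give paracetamol anyway, comparator care differs between centres, and those giving it depart from the written rule.

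**Working it through.** **Does other text restore scheduled paracetamol for TEA patients?** The places that bear on it:

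| Protocol section | What it provides | Restores scheduled paracetamol? |
|---|---|---|
| 5.1, preoperative analgesics | One 1000 mg dose before surgery, all patients | No, a single dose |
| 5.2, usual care for pain management | Unspecified extra medication around the provisional stop ("despite additional pain medication, the TEA can stay in place and the epidural infusion is resumed") | No, drug and schedule not named |
| 5.4 | Escape treatment in the recovery room: epidural bolus, opioids, clonidine or esketamine | No, reactive |
| 8.3 | Paracetamol in a list of oral painkillers, no arm restriction | No, without dose or schedule |
| 12.2.2, pain techniques | TEA according to local anaesthesia guidelines | No, left to the centre |

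None expressly overrides the specific rule in 5.5.

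**What was probably meant?** Section 5.2 says that if rescue of the epidural fails, "opioids may be withdrawn from the epidural solution and oral or intravenous opioids will be supplied". That is the same trigger as in 5.5, and it concerns systemic opioids only. The two passages together point to an exception meant for oxycodone.

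**Reproducing the stated minimum of 11 scores (section 8.1.1).** Section 8.3 sets three diary windows per day: morning 2:00-12:00, afternoon 12:01-18:00, evening 18:01-1:59.

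- Ward scores: POD 0 evening (1) + POD 1 to 3 (3 × 3 = 9) = 10
- Recovery room: 1
- Total: 10 + 1 = 11, as stated

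**Ward scores taken while the opioid-containing epidural runs.** Assumption, not in the protocol: the infusion starts between 08:00 and 16:00 on the day of surgery and stops at exactly 48 hours, so between 08:00 and 16:00 on POD 2.

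- Stop before the POD 2 morning score: 1 (POD 0 evening) + 3 (POD 1) = 4; 4/11 = 36.4%
- Stop after the POD 2 morning score: 4 + 1 = 5; 5/11 = 45.5%
- Stop after the POD 2 afternoon score: 5 + 1 = 6; 6/11 = 54.5%

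The recovery-room score is left out because the preoperative dose in 5.1 may cover it. Including it gives 5 to 7 of 11.

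**Other counting rules.**

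- With the POD 0 afternoon score of Table 1 added: 11 ward + 1 recovery = 12 scores, of which 5 to 7 are affected (5/12 = 41.7%, 7/12 = 58.3%).
- With rest and movement scores both counted: 2 × 10 + 1 = 21 scores, of which 8 to 12 are affected (8/21 = 38.1%, 12/21 = 57.1%).

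**Drug at stake on the literal reading.** 4 × 1 g × 2 days = up to 8 g of scheduled paracetamol per TEA patient by 48 hours.

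These figures measure exposure. The protocol gives no effect of paracetamol on the proportion of NRS scores of 4 or more, so they cannot be turned into a bias.

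**The case against.** The strongest reply is that the literal reading is not the best one. The section begins with a regime for each patient, the trigger makes sense only for an opioid, section 8.3 lists paracetamol with no arm restriction, and TEA care follows local guidelines. Many sites would give paracetamol regardless, and section 5.5 requires all analgesics to be recorded in the CRF. This stands as an account of intent, and it makes the problem one of drafting. It does not remove the problem: the only rule with a dose and a schedule still says otherwise, and the CRF would reveal a difference without preventing it.

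The count is also approximate. It depends on assumed times of surgery and stop, and the preoperative dose may partly cover the earliest ward score. This stands, and it is why a range is given.

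Three stronger readings are tempting and are not supported:

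- A reader might infer that PVB is favoured overall. TEA patients have a continuous epidural with boluses, and section 11.4 expects more episodes of NRS 4 or more with PVB.
- A reader might infer that the early-removal-plus-TEA arm falls outside the exception, because section 10.4 uses control group for late tube removal. Section 10.4 is about recurrence; in a pain section, in a sentence about TEA, the term plainly means TEA patients.
- A reader might infer that a failed epidural leaves a patient with no analgesic plan. Section 5.2 provides for it: "In case the epidural catheter is accidentally removed or is not placed correctly, the patient will receive systemic analgesia".

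**Conclusion.** The point holds as a drafting error in a stated rule. As written, section 5.5 gives the non-inferiority comparator less background non-opioid analgesia than the PVB arms for the planned 48 hours of opioid-containing epidural. This spans roughly 4 to 6 of the minimum 11 POD 0-3 scores (36-55%), assuming daytime surgery and a stop at 48 hours.

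If sites follow the text, that component eases a finding of non-inferiority; if they do not, practice may vary by centre. Which of these happens depends on how sites read one sentence. Neither the size of a bias nor a net direction for the whole comparison can be derived from the protocol. Withholding oxycodone while the epidural contains an opioid is not questioned. It is a minor correction, worth making because it touches a primary outcome.

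**What to change.** Reword section 5.5 along these lines: paracetamol 1000 mg four times daily is given to all patients in all four arms from POD 0. Oxycodone 5-10 mg up to six times daily as needed is given to all patients except while an opioid-containing epidural infusion is running; it may start once the infusion is stopped, the TEA is removed, or the epidural solution contains no opioid.

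Naming a stopped infusion is deliberate. Section 5.2 plans a provisional stop that can leave the catheter in place, and the current triggers mention only removal or an opioid-free solution. Escape medication in section 5.4 stays as it is.

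The cost is a wording amendment and a letter to sites, with no extra patients, procedures or data.

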#### **5.6 Follow up**

After surgery, patients will be admitted to the ward. After chest tube removal and TEA removal (in case this is performed), patients may be discharged in case of sufficient pain control (NRS  $<4$ ) with oral pain medication and sufficient self-care. In case patients fulfil the discharge criteria but remain admitted to the hospital, the reasons will be noted. During hospital stay patients will complete a diary for at least POD 0-3 (for pain scores, quality of recovery and EQ-5D health status). In case of discharge before POD 3, patients will complete their diary at home for at least POD 0-3. After 4 weeks, patients will be seen at the outpatient clinic in order to actualize postoperative morbidity, pain, QoR, QLQ-C30 and EQ-5D-5L. Also, diaries will be collected. After 3 months and 1 year patients will be contacted by telephone through the outpatient clinic to actualize for ipsilateral pneumothorax recurrences, to evaluate the presence of thoracic pain with pain scores and the QLQ-C30 and EQ-5D-5L will be registered. For cost-effectiveness analyses adjusted iMTA questionnaires, the Dutch Medical Consumption Questionnaire (DMCQ) and Productivity Cost Questionnaire (PCQ), will be completed at baseline, 1 month, 3 months and 1 year after surgery.

### **6. INVESTIGATIONAL PRODUCT**

Not applicable

### **7. NON-INVESTIGATIONAL PRODUCT**

Not applicable

## 8. METHODS

### 8.1 Study parameters/endpoints

#### 8.1.1 Main study parameter/endpoint

As explained in the sample size section, we discussed the relevance and importance of several outcome measure with a patient panel. Although we expect the largest advantage of our interventions to be a shortened LOS with high impact on cost-effectiveness, the patient panel emphasized that short LOS is important but inferior to recurrence rate of pneumothorax. Next to recurrence rate, patients indicated acute postoperative pain to be an important topic as well. Lastly, patients emphasized uniformity in chest tube policy, the necessity of having a bladder catheter and uniformity in radiology assessments as important factors as well. Together with the patient panel we made the following ranking: 1) recurrence rate; 2) postoperative acute pain; 3) LOS; 4) uniformity in chest tube policy; 5) the need for a urinary catheter; and 6) uniformity in radiologic assessments (CT and X-ray). In addition, the reference panel of Patiëntenfederatie Nederland advised us during the subsidy application to include QoL as outcome parameter in our study.

Primary outcomes:

1. Safety outcome: absolute number of patients with recurrence (maximum allowable difference between early and late chest tube removal groups of 9 recurrences) defined as having an ipsilateral recurrent pneumothorax after chest tube removal, confirmed by X-ray or CT within 1-year, requiring reintervention (either tube thoracostomy or reoperation) or hospital readmission.
2. The primary outcome measure (non-inferiority) for our second intervention (single-shot PVB) will be the proportion of NRS  $\geq 4$ , defined as the number of NRS scores  $\geq 4$  divided by the total number of NRS measurements obtained during POD 0-3. A minimum of 11 NRS pain scores will be collected (1 at the recovery room, and 10 afterwards on the ward).
3. The primary outcome measure for our both interventions (early chest tube removal and single-shot PVB) will be LOS, defined as the total number of in-hospital days including readmissions due to complications or recurrence within 30 postoperative days. The day of surgery will be POD 0. Discharge criteria are: absence of chest tube, sufficient pain control (NRS $<4$ ) with oral pain medication, absence of fever ( $< 38.5$  °C) and being able of self-care.

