The shortened LOS however is only acceptable in case recurrence rates are equal between the early and late chest tube removal groups (patients' perspective). Therefore, three interim analyses will be performed under supervision of a DSMB after 90, 180 and 270 patients who completed 30-day follow-up. When the incidence of recurrences after early chest tube removal exceeds the incidence after late tube removal by more than 9 cases, then early tube removal will no longer be applied and the study will continue with the two late tube removal subgroups, unless the DSMB advises otherwise. The maximum allowable skewness of 9 extra recurrences after early tube removal is based on the following considerations. First, pneumothorax is not directly life threatening and 9 recurrences extra give a modest maximum excess of 5.49% (9/164). Second, a higher excess incidence ( $\geq 10$ ) leads to a decrease in expected savings in LOS by well more than 20%, and undermines the economic benefit of early tube removal too much (164 early removals save 230 hospital days and  $\geq 10$  extra recurrences reduce this gain with a least 50 days).

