#### **9.2.2 Serious adverse events (SAEs)**

A serious adverse event is any untoward medical occurrence or effect that

1. results in death;
2. is life threatening (at the time of the event);
3. requires hospitalisation or prolongation of existing inpatients' hospitalisation;
4. results in persistent or significant disability or incapacity;
5. is a congenital anomaly or birth defect; or
6. any other important medical event that did not result in any of the outcomes listed above due to medical or surgical intervention but could have been based upon appropriate judgement by the investigator.

An elective hospital admission will not be considered as a serious adverse event.

The investigator will report all SAEs to the sponsor without undue delay after obtaining knowledge of the events, except for the following SAEs (that will be listed but not reported):

1. Regular postoperative complications after VATS pleurodesis: wound infection or dehiscence, fever, bleeding, prolonged postoperative air leakage (>5 days), pneumonia, urinary tract infection, thoracic empyema, thromboembolic events and cardiac arrhythmias.
2. Complications related to the study groups (TEA and PVB): infection at the site of injection and post-puncture spinal headache.
3. In case any of those complications occur needing readmission, we will also list them but not report them.

The local investigators are responsible for reporting SAEs. All SAEs, whether or not considered to be related to the study treatment, must be reported by e-mail to

[[contact]](mailto:[contact]) within 24 hours, using the completed SAE report form.

The sponsor will report the SAEs through the web portal *ToetsingOnline* to the accredited METC that approved the protocol, within 7 days of first knowledge for SAEs that result in death or are life threatening followed by a period of maximum of 8 days to complete the initial preliminary report. All other SAEs will be reported within a period of maximum 15 days after the sponsor has first knowledge of the serious adverse events.

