**10.4 Interim analysis**

During the study period 3 interim analysis will be performed under supervision of a DSMB (see *chapter 9.5 Data Safety Monitoring Board*). The interim analysis will take place after 90, 180 and 270 patients who completed 30-day follow-up. In the intervention group (early tube removal) and the control group (late tube removal) the amount of early recurrences will be assessed. In case the intervention group exceeds the maximum allowable skewness of 9 extra recurrences, the early tube removal group will be stopped. The definition for a recurrence is an ipsilateral recurrence confirmed by X-ray or CT-scan and requires any kind of treatment.

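### A pneumothorax managed without drain or reoperation counts as a recurrence only if it causes readmission, so the primary safety count depends on discharge timing, which both randomised factors influence

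*Protocol*

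**What the plan says.** Section 8.1.1, item 1, makes recurrence a primary (safety) outcome, "defined as having an ipsilateral recurrent pneumothorax after chest tube removal", and qualifying only when "confirmed by X-ray or CT within 1-year, requiring reintervention (either tube thoracostomy or reoperation) or hospital readmission". The decision limit is a raw count: "maximum allowable difference between early and late chest tube removal groups of 9 recurrences". A longer index stay is not a qualifying event.

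Discharge is tied to both randomised factors. Section 5.6 states: "After chest tube removal and TEA removal (in case this is performed), patients may be discharged in case of sufficient pain control". Section 5.3 allows tube removal from 4 hours after surgery in the early groups; section 5.2 allows it from POD 3 in the late groups. For the epidural, section 5.2 says "A provisional stop of the administration of the epidural infusion is planned after 48 hours (on the second postoperative day", with a possible extension to at most 4 days, and section 8.3 keeps the catheter in for at least 2 days. PVB patients have no catheter.

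Section 10.4, which describes the interim looks under the same 9-case limit, defines the event differently: "The definition for a recurrence is an ipsilateral recurrence confirmed by X-ray or CT-scan and requires any kind of treatment". Section 9.2.2 classes an event as serious if, among other criteria, it "requires hospitalisation or prolongation of existing" hospital stay, and recurrent pneumothorax is not on its list of exempt complications.

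**The concern.** A patient who has not left hospital cannot be readmitted. Take the same pneumothorax, confirmed on imaging after tube removal and managed without drain or reoperation. Before discharge it is not a recurrence under 8.1.1; after discharge, if the patient is brought back in, it is. The classification turns on where the patient happens to be.

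That would matter little if time in hospital after tube removal were similar across arms, but the protocol's own rules make it depend on allocation. An early + TEA patient may be without a tube from 4 hours and still have to wait for the epidural to come out. In the other three arms discharge may follow tube removal more closely. Events could then be missed more often in one of the two early-removal cells, which would make early removal look safer than it is and make recurrence appear to vary with the analgesic technique.

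The outcome is the one the patient panel ranked first. It is judged on a difference of 9 cases, in an open-label trial where readmission is partly a matter of judgement. The second definition in 10.4 adds to the problem, because one event can be classified differently at the interim looks and in the final analysis.

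**Working it through.** **The plan's own figure.** 9/164 = 0.0549, which reproduces the stated rate: "9 recurrences extra give a modest maximum excess of 5.49% (9/164" in the early group). With 164 per tube group, each of the four cells has 82 completers.

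**Earliest in-hospital time after tube removal, from sections 5.2, 5.3, 5.6 and 8.3**

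| Arm | Tube out from | Epidural out from | Possible wait after tube removal |
|---|---|---|---|
| Early + TEA | 4 h | about 48 h | up to 48 - 4 = 44 h |
| Early + PVB | 4 h | none | none imposed by a catheter |
| Late + TEA | POD 3 | about 48 h, at most 4 days | none on the planned stop; some if TEA is extended |
| Late + PVB | POD 3 | none | none imposed by a catheter |

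These are earliest permitted times, not expected ones.

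**Size, under stated assumptions.** The protocol gives no rate of conservatively managed pneumothorax, so this is a range.

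- Late recurrence rate: 5.57% (section 5.3, systematic review).
- True excess set at the limit: early rate = 5.57% + 5.49% = 11.06%.
- u = share of early + TEA patients whose event goes uncounted. v = the same share in each late cell. Early + PVB is assumed to lose none.
- Events lost from early + TEA = 82u.
- Shift in the expected early-minus-late count = -82u + 2 × 82v.
- P(observed excess ≤ 9) comes from exact convolution of the four binomial counts, n = 82 each.

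| u | Events lost, early + TEA | P(excess ≤ 9), v = 0 | P(excess ≤ 9), v = u/2 |
|---|---|---|---|
| 0 | 0 | 0.543 | 0.543 |
| 0.25% | 82 × 0.0025 = 0.2 | 0.559 | 0.543 |
| 0.5% | 82 × 0.005 = 0.4 | 0.576 | 0.544 |
| 1% | 82 × 0.01 = 0.8 | 0.608 | 0.544 |

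With v = u/2 the expected shift is -82u + 2 × 82 × u/2 = 0, and the probability stays at about 54%. With v above u/2 the shift would go against early removal.

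**The two definitions side by side.** Section 8.1.1 requires a drain, reoperation or readmission. Section 10.4 requires any treatment and has no readmission condition. An event treated by something short of a drain or reoperation during the index stay counts in 10.4 but not in 8.1.1. An event readmitted for observation alone counts in 8.1.1 and, if observation is not treatment, not in 10.4. Both are compared with 9.

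**The case against.** Requiring an intervention or a readmission is a defensible severity threshold, and events that need a drain or reoperation count in every arm and setting. The affected group is narrow: the event must follow tube removal, precede discharge, need no drain or reoperation, and yet be one that would have led to readmission from home. The only short-term figure in the protocol, 1% tube reinsertion within a week in a single cohort (section 5.3), concerns events that count anyway. Such events could also be found through other records: reasons for staying once discharge criteria are met (5.6), extra imaging with reasons and Clavien-Dindo morbidity (8.1.2), and SAE reports (9.2.2). The interim definition has no readmission condition, so the interim looks as described in 10.4 do not carry this asymmetry. All of this stands and keeps the point modest. None of it makes the final count in 8.1.1 independent of discharge timing.

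A reader might infer something stronger: that events are lost from early + TEA alone, so that the bias certainly favours early removal and is large. At u = 1%, 2% and 3% with no loss elsewhere, the probability would be 61%, 67% and 73%. The documents do not support that. It sets the wait to its maximum in one arm and to zero in three. The X-ray needed for removal may come as late as the morning of POD 1, which shortens the 44 hours. Discharge also requires oral pain control, no fever and self-care, so patients in any arm may wait. TEA may run to 4 days, so late + TEA patients may wait after tube removal. The planning mean stay for late removal is 5.3 days, beyond the earliest removal at POD 3, although part of that may be prolonged drainage. A rate of 3% would be 3/4.59 = 65% of the whole early-removal recurrence rate in the systematic review.

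**Conclusion.** The point holds as a weakness in the endpoint definition. The readmission criterion makes the primary safety count depend partly on discharge timing, which allocation influences, and no other section repairs this for the final analysis. Under-counting of early removal is the most plausible direction, because the early + TEA cell has the longest potential wait after tube removal, but the net direction is not established. The illustrative size is 0.2-0.8 lost events against a limit of 9, moving the probability of staying within the limit from 54% to 56-61%. This rests on an assumed event rate of 0.25-1% and on no losses in the other arms; the net effect disappears if each late cell loses half as many. The mismatch between 8.1.1 and 10.4 stands on the text alone and needs no assumption. Both are worth correcting because correction is cheap, not because a large bias has been shown.

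**What to change.** Use one recurrence definition in 8.1.1 and 10.4, with criteria that do not depend on whether the patient has been discharged. For example:

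- **Count compared with the limit of 9:** imaging-confirmed ipsilateral pneumothorax after tube removal requiring tube thoracostomy or reoperation, in any setting.
- **Prespecified supporting count:** the above plus conservatively managed events, whether they occurred during the index admission (stay prolonged or not) or led to readmission. One CRF item for the index stay captures these.

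Adding prolongation of the index admission as a further trigger, in line with 9.2.2, looks simpler but does not solve the problem. An event observed while an early + TEA patient is waiting for epidural removal need not lengthen the stay, so it would still be missed, whereas the same event in a patient otherwise ready to leave would register. It would also add a discretionary trigger to an open-label trial.

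Cost: a wording change in two sections, one CRF item and one extra tabulation. Events that qualify only through readmission move from the main count to the supporting count.
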